1.1.3.3. Stage 3A Study Objectives

Objectives of Stage 3A in patients with CMML are:

- To characterize the safety profile of tagraxofusp.
- To obtain preliminary evidence of response to tagraxofusp therapy as assessed by the MDS/MPN 2015 criteria ([Savona 2015](#)), with the addition of a stable disease (SD) category, and to obtain data relative to additional clinical parameters that may be used in determination of therapeutic benefit.

The MDS/MPN 2015 criteria ([Savona 2015](#)) represent the current consensus criteria for evaluation of clinical benefit in patients with CMML, beyond those specified in the IWG-MDS criteria ([Cheson 2006](#)). Thus, as an inherent component of the design of Stage 3A, responses to treatment are being assessed using the MDS/MPN 2015 criteria. The hematology community has recognized that a lack of a SD category in the 2015 MDS/MPN IWG criteria creates

considerable uncertainty in the categorization of patients on any CMML study. Therefore, a SD category, defined as those patients not belonging to any of the defined categories in the 2015 criteria, has been added as a response category.

The purpose of Stage 3A, is to analytically evaluate the clinical benefit derived from individual components, or variations thereof, of the MDS/MPN 2015 criteria that may allow for a prospective definition of a primary efficacy endpoint. Clinical benefit includes erythroid, platelet, neutrophil, spleen, and symptom responses, as defined in Table 8-4 in [Section 8.2](#), as well as transfusion dependence status and symptom score.

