4.3.1. Response Rate

Objective response rate and the corresponding 95% Clopper Exact CIs will be presented as the number and percentage of patients who achieve disease-specific complete response (CR) or partial response (PR) after treatment.

Best overall response will be presented as the number and percentage of patients who achieve disease-specific (see [Section 8](#)) CR, PR, stable disease (SD), progressive disease (PD) or who are not evaluable (NE) as their best response on study.

Swim lane plots will be produced for each disease presenting the time on treatment and in response.

The time from the date of first infusion of tagraxofusp to the date from when criteria are first met for CR or PR will be summarized.

Patients who remain in response per investigator and receive a stem cell transplant will be identified and summarized.

For MF patients, the number and percentage of patients who achieved clinical improvement, anemia, spleen, or symptom responses, molecular remission, or cytogenetic/molecular relapse will also be presented using IWG-MRT/ELN criteria (see [Section 8.1](#) for disease specific response criteria). The time from date of first infusion of tagraxofusp to the date from when each response of clinical benefit criteria (as defined in Table 8-4 in [Section 8.2](#)) are first met will be summarized.

For CMML patients, the number and percentage of patients who achieved erythroid, platelet, neutrophil, spleen or symptoms responses will also be presented (see [Section 8.2](#) for disease specific response criteria). The time from date of first infusion of tagraxofusp to the date from when each category of clinical benefit criteria are first met will be summarized.

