4.3.2. Duration of Response

Duration of objective response is defined as the time from when the disease specific criteria (see [Section 8](#)) are first met for CR or PR until the date that the criteria for relapse (including SD, progressive disease [PD], or relapse) after CR/PR is met, or death. In the case that SD follows CR/PR and there is no evidence that response rebounds to CR/PR, duration of objective response will end at the time of first reduction of response to below CR/PR. For patients who receive SCT after CR/PR, DOR will include time to disease relapse post-transplant. Patients who are lost to follow-up or who do not relapse after objective response as of the analysis date will be censored on the latter of the date of last treatment with tagraxofusp or date of last disease

assessment recorded prior to the analysis date. If patient starts other anticancer therapies (with the exception of SCT), they will be censored at the latter of the date of last treatment with tagraxofusp or date of last disease assessment recorded that occurred prior to the start of the new therapy.

The distribution of DOR will be estimated by Kaplan-Meier methodology and the 25th percentile, median, and 75th percentile of time to event, number and percentage of events and censored observations, and appropriate 95% CIs will be presented.

For MF patients, the median duration of response for each category of clinical benefit, including clinical improvement, anemia, spleen, or symptom responses, molecular remission, or cytogenetic/molecular relapse, will be derived similar to the duration of objective response. For CMML patients, the median duration of response for each category of clinical benefit, including erythroid, platelet, neutrophil, spleen or symptoms responses, will be derived similar to the duration of objective response.

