Progressive disease¹⁰	
Appearance of new splenomegaly that is palpable at least 5cm below the LCM or
 
$A \geq 100\%$ increase in palpable distance, below LCM, for baseline splenomegaly of 5-10 cm or
 
A 50% increase in palpable distance, below LCM, for baseline splenomegaly of > 10 cm or
 
Leukemic transformation confirmed by a bone marrow blast count of $\geq 20\%$ or
 
A peripheral blast content of $\geq 20\%$ associated with an absolute blast count of $\geq 1 \times 10^9/L$ that lasts for at least 2 weeks

Stable disease	Belonging to none of the above listed response categories
Relapse	
No longer meeting criteria for at least CI after achieving CR, PR or CI, or
 
Loss of anemia response persisting for at least 1 month or
 
Loss of spleen response persisting for at least 1 month

Cytogenetic remission	
At least 10 metaphases must be analyzed for cytogenetic response evaluation and requires confirmation by repeat testing within a 6-month window
 
CR: eradication of a preexisting abnormality
 
PR: $\geq 50\%$ reduction in abnormal metaphases (partial response applies only to patients with at least 10 abnormal metaphases at baseline)

Molecular remission	
Molecular response evaluation must be analyzed in peripheral blood granulocytes and requires confirmation by repeat testing within a 6-month window
 
CR: eradication of a preexisting abnormality
 
PR: $\geq 50\%$ decrease in allele burden (partial response applies only to patients with at least 20% mutant allele burden at baseline)

Cytogenetic/molecular relapse	Re-emergence of a pre-existing cytogenetic or molecular abnormality that is confirmed by repeat testing

Adapted from Tefferi, et al. Blood 2013; 122(8):1395-98.

EMH: extramedullary hematopoiesis (no evidence of EMH implies the absence of pathology- or imaging study-proven nonhematosplenic EMH). LCH: left costal margin. ULN: upper limit of normal.

1 Baseline and posttreatment bone marrow slides are to be interpreted at one sitting by a central review process. Cytogenetic and molecular responses are not required for CR assignment.

2 Grading of MF is according to the European classification. Thiele et al. European consensus on grading bone marrow fibrosis and assessment of cellularity. Haematologica 2005; 90: 1128.

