It is underscored that the consensus definition of a CR bone marrow is to be used only in those patients in which all other criteria are met, including resolution of leukoerythroblastosis. It should also be noted that it was a particularly difficult task for the working group to reach a consensus regarding what represents a complete histologic remission.

- 3 Immature myeloid cells constitute blasts + promyelocytes + myelocytes + metamyelocytes + nucleated red blood cells. In splenectomized patients, < 5% immature myeloid cells is allowed.
- 4 See above for definitions of anemia response, spleen response, and progressive disease. Increase in the severity of anemia constitutes the occurrence of new transfusion dependency or a ≥ 20 g/L decrease in hemoglobin level from pretreatment baseline that lasts for at least 12 weeks. Increase in severity of thrombocytopenia or neutropenia is defined as a 2-grade decline, from pretreatment baseline, in platelet count or absolute neutrophil count, according to the CTCAE version 4.03. In addition, assignment to CI requires a minimum platelet count of $\geq 25 \times 10^9$ /L and absolute neutrophil count of $\geq 0.5 \times 10^9$ /L.
- 5 Applicable only to patients with baseline hemoglobin of < 100 g/L. In patients not meeting the strict criteria for transfusion dependency at the time of study enrollment (see as follows), but have received transfusions within the previous month, the pretransfusion hemoglobin level should be used as the baseline.
- 6 Transfusion dependency before study enrollment is defined as transfusions of at least 6 units of pRBCs in the 12 weeks prior to study enrollment, for a hemoglobin level of < 85 g/L, in the absence of bleeding or treatment-induced anemia. In addition, the most recent transfusion episode must have occurred in the 28 days prior to study enrollment. Response in transfusion-dependent patients requires absence of any pRBC transfusions during any consecutive “rolling” 12-week interval during the treatment phase, capped by a hemoglobin level of ≥ 85 g/L.
- 7 In splenectomized patients, palpable hepatomegaly is substituted with the same measurement strategy.
- 8 Spleen or liver responses must be confirmed by imaging studies where a $\geq 35\%$ reduction in spleen volume, as assessed by MRI or CT, is required. Furthermore, a $\geq 35\%$ volume reduction in the spleen or liver, by MRI or CT, constitutes a response regardless of what is reported with physical examination.

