Adapted from Cheson, et al. Blood 2006; 108(2):419-25.

Deletions to the IWG response criteria are not shown. To convert hemoglobin from g/dL to g/L, multiply g/dL by 10. MDS: myelodysplastic syndromes. Hgb: hemoglobin. CR: complete remission. HI: Hematologic improvement. PR: partial remission. FAB: French-American-British. AML: Acute myeloid leukemia. PFS: Progression-free survival. DFS: Disease-free survival.

- 1 Dysplastic changes should consider the normal range of dysplastic changes (modification) (Ramos 1999)
- 2 Modification to IWG response criteria
- 3 In some circumstances, protocol therapy may require the initiation of further treatment (e.g., consolidation, maintenance) before the 4-week period. Such patients can be included in the response category into which they fit at the time the therapy is started. Transient cytopenias during repeated chemotherapy courses should not be considered as interrupting durability of response, as long as they recover to the improved counts of the previous course.

Table 8-4 Stage 3A: 2015 MDS/MPN Response Criteria (Savona 2015)

Criteria for measurement of treatment response in adult MDS/MPN

CR (presence of all of the following improvements)¹

- Bone marrow:
 - $\leq 5\%$ myeloblasts (including monocytic blast equivalent in case of CMML)
 - Normal maturation of all cell lines and return to normal cellularity¹
 - Osteomyelofibrosis absent or equal to “mild reticulin fibrosis” (\leq grade 1 fibrosis)²
- Peripheral blood³
 - $WBC \leq 10 \times 10^9$ cells/L
 - $Hgb \geq 11$ g/dL
 - Platelets $\geq 100 \times 10^9/L; \leq 450 \times 10^9/L$
 - Neutrophils $\geq 1.0 \times 10^9/L$
 - Blasts 0%
 - Neutrophil precursors reduced to $\leq 2\%$
 - Monocytes $\leq 1 \times 10^9/L$
- Extramedullary disease: Complete resolution of extramedullary disease present before therapy (e.g. cutaneous disease, disease-related serous effusions), including palpable hepatosplenomegaly
- Persistent low-level dysplasia is permitted given subjectivity of assignment of dysplasia¹

Note: Provisional category of CR with resolution of symptoms is removed from the original criteria.³

Complete cytogenetic remission

- Resolution of previously present chromosomal abnormality (known to be associated with myelodysplastic, syndrome myeloproliferative neoplasms, or MDS/MPN), as seen on classic karyotyping with minimal of 20 metaphases or FISH⁴

Criteria for measurement of treatment response in adult MDS/MPN

Partial remission

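### SAP 4.3.1 times MF component responses by the CMML table, 4.3.2 gives relapse a duration of response, and cytogenetic remission has no planned summary

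*SAP*

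**What the plan says.** SAP 4.3.1 has one paragraph on component responses for MF and a parallel one for CMML.

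- **MF, rates.** The number and percentage of patients who achieved "clinical improvement, anemia, spleen, or symptom responses, molecular remission, or cytogenetic/molecular relapse will also be presented", and the criteria named are IWG-MRT/ELN with a pointer to Section 8.1.
- **MF, times.** The next sentence summarises time from first infusion to when "each response of clinical benefit criteria (as defined in Table 8-4 in" Section 8.2) are first met.
- **CMML, times.** The matching sentence in the CMML paragraph names no table.

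The table cited for MF times is headed "Stage 3A: 2015 MDS/MPN Response Criteria". SAP 1.1.3.3, on the Stage 3A CMML objectives, uses it in that sense: "Clinical benefit includes erythroid, platelet, neutrophil, spleen, and symptom responses, as defined in Table 8-4 in" Section 8.2.

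SAP 4.3.2 then gives MF patients a median duration of response for each category of clinical benefit. The list runs to "spleen, or symptom responses, molecular remission, or cytogenetic/molecular relapse", each derived in the same way as the duration of objective response.

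Table 8-1 in SAP 8.1 defines cytogenetic remission at CR and PR levels, with the condition "At least 10 metaphases must be analyzed for cytogenetic response evaluation". It defines cytogenetic/molecular relapse as the confirmed return of an abnormality that was there before.

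**The concern.** A rate table and a time-to-response table for the same patients should describe the same responders. Here two adjacent sentences send the programmer to two sets of criteria, written for two diseases. Followed as written, the MF time-to-response table could contain patients who are not responders in the rate table, omit some who are, and have no rule for two of the listed categories.

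The duration list has a separate fault: it treats a loss of remission as a benefit that lasts. A category that is a remission, and for which samples are scheduled, appears in neither list.

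SAP 5 and the revision history show that the times and component durations were added deliberately, and SAP 3.12 makes this document the basis of the final study-report analyses. The text is therefore likely to be programmed.

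**Working it through.** No figure in the plan is at issue, so the check is a comparison of definitions.

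**1. The two tables, item by item**

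| Item | Table 8-1 (MF) | Table 8-4 (Stage 3A CMML) |
|---|---|---|
| Persistence | benefit of at least 12 weeks | verified at 8 weeks or later |
| Hemoglobin rise | at least 20 g/L; "Applicable only to patients with baseline hemoglobin of < 100 g/L" | at least 2.0 g/dL; no baseline limit |
| Transfusion independence | any 12-week interval | at least 8 weeks |
| Spleen | imaging confirmation of at least 35% volume reduction; that reduction alone also qualifies | defined by palpation |
| Symptoms | at least 50% reduction in MPN-SAF TSS; no minimum score | at least 50% reduction; scores below 20 not eligible |
| Platelet, neutrophil response | none | defined |
| Clinical improvement, molecular remission | defined | none |

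**2. The discrepancy runs both ways**

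- *Counted only under Table 8-4.* Take an MF patient with no transfusions, progression or CR/PR, whose hemoglobin rises from 115 to 136 g/L for 9 weeks. The rise is 136 − 115 = 21 g/L = 2.1 g/dL, which is at least 2.0 g/dL, and 9 weeks is at least 8: an erythroid response under Table 8-4. Under Table 8-1 the patient fails twice, since 115 is not below 100 and 9 is less than 12.
- *Counted only under Table 8-1.* A spleen volume reduction of at least 35% lasting 12 weeks, without the palpation change that Table 8-4 requires, is an MF spleen response only. The same holds for a halved symptom score when the baseline score was below 20.
- *Undefined.* Time to clinical improvement or to molecular remission cannot be derived from Table 8-4.

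**3. Relapse in the duration list**

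SAP 4.3.2 runs the duration of objective response from the first date the response criteria are met to relapse, progression or death, and applies the same derivation to each listed category. If the category is itself a relapse, the starting event is of the kind that should end the interval. No response is being timed.

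**4. Cytogenetic remission**

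SAP 4.3.1 and 4.3.2 list molecular remission but not cytogenetic remission. No summary of it appears in 1.2.5.1 or in 4.3.3 to 4.3.8, and SAP 5 does not declare it dropped. Cytogenetic testing is nevertheless scheduled at screening, at the end of cycles 1 and 4, every 12 weeks thereafter and at end of treatment (SAP Tables 7-1 and 7-2). Evaluating specific components of these criteria is a stated MF objective (SAP 1.1.3.2).

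**The case against.** The strongest reply is that the intent can be recovered. SAP 1.2.5.1 assigns anemia, spleen and symptom responses to MF, and erythroid, platelet, neutrophil, spleen and symptom responses to CMML. SAP 4.3.7 keeps anemia response for MF apart from erythroid response for CMML. The CMML sentence in 4.3.1 lacks a table reference, which suggests that the Table 8-4 reference was placed one paragraph too early. This is probably how it happened, and a careful programmer might catch it. It does not change what the sentence instructs.

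Other parts of the reply narrow the point, and they stand:

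- A reader might infer that the MF component results as a whole are wrong. They are not. The rates "will also be presented using IWG-MRT/ELN criteria (see" Section 8.1), which is correct for MF.
- The spleen contrast is smaller than the tables alone suggest. Protocol 11.5 requires imaging confirmation of a palpation response in both stages, though it gives no 35% threshold there.
- A reader might infer that cytogenetic remissions would go unreported. Protocol 11.12.1 collects metaphase counts and karyotype in the CRF, and SAP 3.10 puts all eCRF data into listings. What is missing is a planned summary.
- Counting relapses is legitimate, because relapse is a defined row of Table 8-1. Only calling it a response, and giving it a duration as a benefit, is wrong.
- The table shells are in a separate document that was not available, and may already be right.

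**Conclusion.** The point holds for three limited items: the criteria cited for time to MF component response, the duration of response assigned to cytogenetic/molecular relapse, and the absence of a planned summary of cytogenetic remission. The first, read literally, gives times based on different responders from the rates, or no definition at all for clinical improvement and molecular remission. The second has no meaning. The third leaves the MF results incomplete rather than wrong.

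The MF component rates are not affected. Neither are ORR (the primary efficacy endpoint), best overall response, duration of objective response, PFS or OS. The affected summaries are descriptive and secondary, and SAP 3.7 applies no type I error control. This is a minor correction.

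How many MF patients would be classified differently cannot be worked out from the documents. The conclusion assumes that the SAP text is programmed as written; if the table shells already apply Table 8-1, only the text needs to be brought into line.

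**What to change.** - **SAP 4.3.1, MF paragraph:** cite Table 8-1 in Section 8.1 for time to response, and time only the responses counted in the rate table.
- **SAP 4.3.1, CMML paragraph:** move the Table 8-4 reference here, for Stage 3A.
- **SAP 4.3.1 and 4.3.2, MF lists:** add cytogenetic remission.
- **SAP 4.3.2, MF list:** remove cytogenetic/molecular relapse from the categories of clinical benefit, and use it as the event that ends a cytogenetic or molecular remission.
- **SAP 4.3.1, relapse count:** if it is kept, show it as a separate item that is not labelled a response. Putting cytogenetic remission in its place would lose a legitimate count.

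The cost is a few wording edits and a check of the matching table shells. No new data are needed.

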4.3.2. Duration of Response

Duration of objective response is defined as the time from when the disease specific criteria (see [Section 8](#)) are first met for CR or PR until the date that the criteria for relapse (including SD, progressive disease [PD], or relapse) after CR/PR is met, or death. In the case that SD follows CR/PR and there is no evidence that response rebounds to CR/PR, duration of objective response will end at the time of first reduction of response to below CR/PR. For patients who receive SCT after CR/PR, DOR will include time to disease relapse post-transplant. Patients who are lost to follow-up or who do not relapse after objective response as of the analysis date will be censored on the latter of the date of last treatment with tagraxofusp or date of last disease

assessment recorded prior to the analysis date. If patient starts other anticancer therapies (with the exception of SCT), they will be censored at the latter of the date of last treatment with tagraxofusp or date of last disease assessment recorded that occurred prior to the start of the new therapy.

The distribution of DOR will be estimated by Kaplan-Meier methodology and the 25th percentile, median, and 75th percentile of time to event, number and percentage of events and censored observations, and appropriate 95% CIs will be presented.

For MF patients, the median duration of response for each category of clinical benefit, including clinical improvement, anemia, spleen, or symptom responses, molecular remission, or cytogenetic/molecular relapse, will be derived similar to the duration of objective response. For CMML patients, the median duration of response for each category of clinical benefit, including erythroid, platelet, neutrophil, spleen or symptoms responses, will be derived similar to the duration of objective response.

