CMML patients will be classified as “dependent” or “independent” at baseline within each category of platelets, packed red blood cells (pRBC), and both (i.e., receiving both platelets and pRBC) if they received transfusions of at least 4 units in the 8 weeks prior to the study enrollment. Transfusion independence for CMML will be defined as patients who experience at least a 8 week period during any point on treatment with no transfusion of that type required.

Secondary Efficacy Endpoints

The secondary efficacy endpoints are DOR, PFS, OS, and duration of follow-up.

Duration of objective response is defined as the time from when criteria are first met for CR or PR until the date that the criteria for relapse is met. Progression-free survival is defined as the time from the date of first infusion of tagraxofusp to the date of PD or death from any cause. Overall survival is defined as the time from the date of first infusion of tagraxofusp to the date of death from any cause.

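### In MF and Stage 3A CMML, the duration-of-response rule does not stop when CR/PR is lost to an intermediate response category, so DOR can be overstated

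*SAP*

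**What the plan says.** SAP 4.3.2 starts DOR when the disease-specific criteria of Section 8 are first met for CR or PR. DOR runs "until the date that the criteria for relapse (including SD, progressive disease [PD], or relapse) after CR/PR is met, or death". A second sentence moves the end date back in one situation: "In the case that SD follows CR/PR and there is no evidence that response rebounds to CR/PR", then "duration of objective response will end at the time of first reduction of response to below CR/PR". SAP 1.2.5.1 gives a shorter definition, "until the date that the criteria for relapse is met", and refers to Section 4.3 for detail.

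The terms in that rule are defined by disease:

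- **MF (SAP Table 8-1).** Relapse is "No longer meeting criteria for at least CI after achieving CR, PR or CI", or loss of an anemia or spleen response that persists for at least 1 month. SD is "Belonging to none of the above listed response categories".
- **Stage 3A CMML (SAP 1.1.3.3 and Table 8-4).** The plan adds "a SD category, defined as those patients not belonging to any of the defined categories in the 2015 criteria". Marrow response and clinical benefit are defined categories. The table has no relapse category, and progression needs two major criteria, one major and two minor, or three minor.
- **CMML Stages 1-2 (SAP Table 8-3).** SD is failure to reach at least PR without progression for more than 8 weeks, and the table has its own list for relapse after CR or PR.

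Objective response is CR or PR only (SAP 1.2.5.1 and 4.3.1).

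**The concern.** The endpoint is the duration of CR/PR, so it should end when CR/PR ends. The listed end events leave out the categories that lie between PR and SD. A patient can stop meeting CR and PR, move into one of those categories, and trigger no end event. DOR then runs on to a later PD, relapse, death or censoring date.

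DOR is a named secondary endpoint, reported as Kaplan-Meier quartiles with 95% confidence intervals. Time spent in a lesser response would be reported as time in CR/PR, and the error can only lengthen the estimate. SAP 1.2.5.1 also omits SD, PD and death, so two programmers working from different sections could produce different durations.

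**Working it through.** The documents state no DOR figure to reproduce. The check sets the definitions side by side and then applies the literal rule to assumed paths.

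**Step 1: does a fall to an intermediate state trigger an end event?**

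- *MF, CR/PR to CI.* Suppose disease symptoms return while the spleen response holds. CR and PR both require resolution of symptoms, so both are lost, and the patient still meets CI. CI is a listed category, so the patient is not SD. CI is still met, so the first relapse criterion fails. CI excludes PD. No end event occurs. If an anemia or spleen response is lost for at least 1 month, that is relapse and DOR ends.
- *Stage 3A, CR to marrow response.* Suppose hemoglobin drops below 11 g/dL while every marrow criterion for CR is still met. PR requires normal counts, so the patient is in optimal marrow response. That is a defined category, so not SD. One hemoglobin criterion is a single minor criterion, so not PD. No relapse definition exists. No end event occurs.
- *Stage 3A, CR/PR to clinical benefit.* This category applies only when CR/PR and progression are both absent. It is again not SD and not PD.
- *CMML Stages 1-2.* A state below PR without progression counts as SD once it has lasted more than 8 weeks, and a relapse list exists. The gap largely closes.

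**Step 2: what does the rule return?** Assessment weeks follow from the protocol schedule: end of C1 = 21/7 = week 3; end of C4 = 4 × 21/7 = week 12; then every 12 weeks (24, 36, 48). All paths are assumed: CR first met at week 12. INT stands for CI, marrow response or clinical benefit. DOR = end week − 12.

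| Path after CR at week 12 | SAP 4.3.2 as written | Ending at first unrecovered fall below CR/PR |
|---|---|---|
| INT at 24, SD at 36 | 24 − 12 = 12 if back-dating applies; 36 − 12 = 24 if it does not | 24 − 12 = 12 |
| INT at 24, PD at 36 | 36 − 12 = 24 | 12 |
| INT at 24 and 36, PD at 48 | 48 − 12 = 36 | 12 |
| INT at 24, 36 and 48, then cut-off | 48 − 12 = 36, censored | 12, event |
| SD at 24, PD at 36 | 12 | 12 |
| PD at 24 | 12 | 12 |

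The censored row takes week 48 as the later of last dose and last assessment.

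Table 8-1 requires MF benefit to last at least 12 weeks. For MF, therefore, add a second CR assessment at week 24 and move every later event by 12 weeks. Each result rises by 12 weeks and the excess is unchanged: 36 − 24 = 12 weeks with PD at 48, and 48 − 24 = 24 weeks with PD at 60. Each further 12-weekly assessment spent in the intermediate state adds about 12 weeks.

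**The case against.** The best case for the plan is that SD was meant to cover everything below CR/PR that is not progression. Best overall response in SAP 4.3.1 has only five categories (CR, PR, SD, PD, not evaluable), CI and the component responses are reported separately, and the back-dating sentence speaks of "duration of objective response will end at the time of first reduction of response to below CR/PR". On that reading every path in the table ends at 12 weeks. This may well be the intent. However, SAP 4.3.1 and 4.3.2 both point to Section 8 for the criteria, and in MF and Stage 3A SD is defined as a residual category. The text needs one sentence to say otherwise.

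It is also true that the MF relapse rule is the one in the protocol's own response table. It fits a definition of response that includes CI; it does not fit a duration restricted to CR/PR.

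Some stronger readings are tempting, and the documents do not support them:

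- *A patient who progresses gets a longer DOR than one who stabilises.* This holds only if "In the case that SD follows CR/PR and there is no evidence that response rebounds to CR/PR" includes SD reached after an intervening state. If SD must follow directly, the first path in the table gives 24 weeks, the same as PD at week 36, and the reversal disappears.
- *Counting CR-SD-CR as unbroken is an error.* It is an explicit rebound rule. It is in keeping with Table 8-3 footnote 3, under which transient cytopenias that recover do not interrupt a response.
- *The component durations are biased too.* They are derived similarly, but no corresponding step from CR/PR to a lower category has been shown for them.
- *All CMML results are affected.* Stages 1-2 largely are not.

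On weight: the analysis is descriptive, no Type I error control applies, Stage 3A enrolment was stopped, and Stage 3B will not start. By-patient listings and swim-lane plots would show such paths to a careful reader.

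**Conclusion.** The definition is wrong as written for MF and for Stage 3A CMML. Read with Section 8, SAP 4.3.2 does not end DOR when CR/PR gives way to CI (outside the 1-month anemia or spleen loss rule), marrow response or clinical benefit. The reported duration of CR/PR can therefore be too long.

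The size cannot be computed. The documents give neither the number of CR/PR patients nor the number of these transitions. The 4 of 36 responses described in the protocol are bone marrow complete responses, which Table 8-3 lists as a category separate from CR and PR. The 12- and 24-week excesses above are consequences of assumed paths. The conclusion rests on taking the Section 8 definitions literally, as SAP 4.3.2 directs. For a descriptive secondary endpoint this is a should-fix point.

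**What to change.** Keep the rebound rule and extend it to every lower category. Suggested text for SAP 4.3.2:

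> DOR ends at the first disease assessment at which the response is below CR/PR (SD, clinical improvement, marrow response or clinical benefit) with no later return to CR/PR, or at PD, relapse or death, whichever is first. Transient cytopenias that recover, as in Table 8-3 footnote 3, do not end response.

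Use the same wording in SAP 1.2.5.1. A version that ends DOR at the first assessment outside CR/PR, whether or not response returns, may be shown as a sensitivity analysis. As a main rule it would override the plan's rebound rule and could turn one transient drop in counts into an event.

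The cost is one SAP paragraph, a matching edit in 1.2.5.1 and a programming change, with no added assessments. The downside is that reported DOR may be somewhat shorter.
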